#### **Pilot Feasibility of ANBL in Urban and Reservation based Tribes in Kansas**

Our American Cancer Society (RSGT-06-260-01-CPPB: PI: [name]) funded grant is a 3 year pilot/feasibility study of ANBL with all program components. The ANBL program components include an initial individual session along with 8 weekly group sessions with individual telephone calls between the group sessions. During the previous pilot, we conducted the ANBL program with 5 weekly in person sessions and another version with 8 weekly in person sessions. The overwhelming preference from our participants was for the more intensive 8 weekly in-person group sessions. All of our participants expressed the need to maintain the group support and dynamics in order to maintain long term abstinence. As a result, we decided to implement the 8 session version rather than the smaller number of sessions. This larger pilot study started in 2006 and we have completed 10 groups of AI/AN smokers. In addition to the ANBL program, all participants were offered varenicline as a form of pharmacotherapy. In this pilot, we also added the use of motivational interviewing (MI) counseling throughout the individual phone sessions. Recruitment and retention (approximately 80%) has been very successful. All participants completed surveys for each group session and there have been no refusals among those in attendance. For the first time, we have also collected saliva samples from our participants at baseline, week 12 and 6 months to verify smoking status. The six month smoking abstinence rates are approximately 30% with ANBL in combination with varenicline. Our dropout rates for this larger feasibility pilot study have been between 15-20 % at 6 months.

***These results demonstrate our team's ability to recruit both urban and reservation based AI/AN smokers in the region. In addition, we have successfully shown our team's ability to maintain high recruitment and retention rates for the groups of smokers for the high intensity ANBL program. We have also successfully integrated the use of MI counseling during the individual phone calls and demonstrated acceptance in this population. Our current version of ANBL is more intense compared to the first version of the program. This increase in intensity is a result of participant and facilitator feedback that 5 in-person group sessions was***

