#### **IV. Inclusion/Exclusion Criteria**

##### **Eligibility**

The eligibility criteria listed below will be assessed at the recruitment visit.

Inclusion Criteria	Exclusion Criteria

 
◆ Age 18 years or older
 
◆ Currently enrolled at a Tribal college
 
◆ Have a valid telephone number and email address
 
◆ Willing to participate in all study components
 
◆ Willing to be followed-up for 6 months
 
◆ Self identifies as American Indian or Alaska Native
 
◆ Is a current smoker – self defined
 
	
 
◆ Planning to leave the college within next 6 months
 
◆ Medically ineligible as a result of screening questions
 

Medical Exclusion Criteria

For overall participation
 
 
◆ Medically ineligible as a result of screening questions
 
◆ Participant under the age of 18 years
 

For NRT (Patch, gum, lozenge):
 
 
• History of severe eczema or any serious skin problem if requested nicotine patch
 
• History of severe allergic reaction to the nicotine patch or other skin adhesives
 
• History of heart attack in the last 2 months
 
• Currently experiencing frequent angina or chest pain related to heart
 
• Currently experiencing signs and symptoms of peptic ulcer
 
• Currently receiving medications for rapid or irregular heart beat
 
• Currently experiencing signs and symptoms of severe, uncontrolled high blood pressure
 
 
For Chantix:
 
 
• Pregnant or breast feeding or planning to become pregnant in the next 6 months
 
• Currently using nicotine replacement therapy (NRT)
 
• History of suicide attempt in the past 12 months
 

- History of thoughts of suicide in the past 12 months
- History of thoughts of harming others in the past 12 months

For Zyban:

- Pregnant or breast feeding or planning to become pregnant in the next 6 months
- History of seizure disorder or head trauma
- History of severe allergic reaction to Zyban (also known as Wellbutrin, Bupropion)
- History of eating disorder, such as anorexia or bulimia, which is overeating and throwing up
- Currently taking Wellbutrin, Zyban or any other medications that contain bupropion

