**Anticipated Flow of Participants:**

Telephone Eligibility Screening Interview		
↓		
In-Person Randomization Visit (n=300)		
←      ↓      →		
Web-based weekly		
Sessions	I – ANBL (n=150)	I – FV (n=150)
1	Preparing to quit, pharmacotherapy/nrt, why do people smoke	Assessment of Risk for Heart Disease, pharmacotherapy/nrt
2	Cigarette smoking and Native people, Quit smoking date	Increasing fruit and vegetable consumption, Quit smoking date
3	Coping with Withdrawal	Physical activity
4	Traditional use of tobacco	High blood pressure
5	Stress reduction and relaxation techniques, traditional meditation techniques	Salt and sodium intake
6	Weight management, Healthy American Indian foods, exercise	High Cholesterol
7	Friends and family and quitting smoking, social support	Maintaining healthy weight
8	Staying quit – congratulations Long term maintenance	Low cost healthy eating – fruits and vegetables
Email reminders will be sent before each session so that participants will log in at the appropriate time		
12	End of pharmacotherapy treatment, feedback of program	End of program, feedback

Email reminders will be sent before each session so that participants will log in at the appropriate time		
Month 6	Assessment for current smoking status	Assessment of current smoking status

(Detailed descriptions of the weekly I-ANBL web materials are included in the appendix: will be adapted to integrate tribal college student issues identified during Phase 1 of the study)

- Telephone Screening Intake:** Research Assistants will review inclusion/exclusion criteria, smoking status and basic information about the program. We will not exclude participants who use other forms of recreational tobacco (eg – smokeless tobacco) because, based on our preliminary data, we would be excluding eligible participants if we did so. In addition, community members have encouraged us to be more inclusive for acceptability of the research in the community and make the inclusion criteria less restrictive. Therefore, we will examine use of other tobacco products in a secondary analysis. We estimate screening intake to take 10-15 minutes.

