- Individual In-Person Visit (Randomization):** Potential participants will meet with a research assistant on campus. At this initial in-person visit, the research assistant will have randomization assignments with them so they can inform the participant which arm they have been randomized to for this program. This session will allow research assistants to explain the program and answer any questions the participant may have that he or she may have about the program. Informed consent will also be obtained during this visit. Finally, it allows the research assistant to explain NRT or pharmacotherapy and provide each participant with information. Individuals who consent to participation will be enrolled in the program and will remain in the arm to which he/she is randomized to for the study. Research assistants will collect baseline saliva sample from each participant. Participants will be informed for future samples (week 12 and month 6), we will request mailings of saliva samples so they will be taught how to provide such samples at this baseline visit. Saliva sample kits will be provided via overnight mail with a pre-paid overnight return. Members of our team have used this approach in other phone-based smoking cessation programs with success. Participants will be asked to make a decision about NRT or pharmacotherapy prior to the second web session. Facilitators will answer any questions the participant has and participants will be given the option of having the study physician call them to discuss personal concerns. Estimated time for individual session is 50-60 minutes. Participants who have not yet decided on medication will be asked to do so then. All participants requesting any form of pharmacotherapy will complete the corresponding medical screener. The study physician will review all medical information prior to the first session. After taking part in the initial session, participants will be e-mailed a login to the website prior to their first session. Future surveys will be done via web interface.

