- **6-Month Follow-Up:** At 6-months post-baseline, participants are asked to take part in a final internet session and will receive a \$20 gift card for participation. They will be asked about their smoking status and will be asked to submit a saliva sample. Participants who do not report abstinence from smoking use will be asked if they would like to participate in the full program again. If they choose to participate a second time, they will not be included in *study outcome* measures, though we will track their success. This is done to mimic the real-world situation where a program could be repeated. After the 6-month follow-up, participants will be sent a final anonymous survey about the program via e-mail.

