### Phase 3: Data Analysis and Dissemination

The objectives of this phase are 1) to conduct data analysis and 2) to disseminate the program.

In Year 5, we will complete post-intervention assessments, data analyses and report writing.

Process and outcome data will be presented at scientific conferences and manuscripts will be submitted to peer-reviewed scientific journals. Ultimately, we envision that **I-ANBL**, if efficacious, could be disseminated and

used as a culturally tailored smoking cessation intervention that could be adopted across different tribal colleges.

**Sample Size and Power:** The primary endpoint will be cotinine verified 7-day point prevalence abstinence at Month 6. Per preliminary findings, we expect a 30% cessation rate in the **I-ANBL** arm and a 15% cessation rate in the **I-FV** arm. Using the chi-square test, and the assumptions above, 121 participants in each group will give us 80% power to detect this difference with a type I error rate of 5%.

Given retention rates from our earlier studies, we expect attrition rates to be approximately 20% over the 6 month study period. Therefore, we anticipate needing to enroll 300 participants at baseline in order to have 242 active participants at 6 months.

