**Data Management:** Survey data will be entered into the REDCap system through our website directly by participants or, in the case of the initial interview, the facilitator while s/he is asking the questions. REDCap is an internet-based survey program that allows de-identified and encrypted data to be collected directly on a site. We have used this program in other studies and our Human Subjects Committee has determined that it is a safe and effective way to collect data remotely. It also allows the creation of separate databases for contact information so that we can maintain a numeric study-specific participant number as the only link between the study database and participant contact information. Data management activities will include conversion into proper format for data analysis and recoding. All data management activities will be supervised by [name].

**Cost-effectiveness analysis:** The purpose of our cost-effectiveness analysis is to establish the cost-effectiveness of the I-ANBL program relative to healthy heart diet intervention. While our cost analytic

framework follows the guidelines adopted by the CDC, we will assess costs from the service provider perspective rather than the recommended societal perspective. Given that there is widespread agreement that

the cessation of smoking behavior confers important societal benefits valued far in excess of the costs needed

to produce them, the research expenses needed to fulfill the societal perspective would exceed the benefit of

that approach. Instead, variable costs for each study arm will be valued in the year during which they are incurred. Discounting is not required for the six month intervention period, and research costs (\$20 gift cards) will be excluded from analyses.

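### The program website is the only route described for the month-6 smoking self-report, so a participant who does not log in has no observed self-report even if the mailed saliva kit comes back

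*Protocol*

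**What the plan says.** The Sample Size and Power paragraph and the Measures table define the primary endpoint as cotinine-verified 7-day point prevalence abstinence at month 6. The two components are collected by different routes.

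- **Self-report.** The in-person randomization visit closes with "Future surveys will be done via web interface". The 6-Month Follow-Up item says "At 6-months post-baseline, participants are asked to take part in a final internet session", and smoking status is asked there. The Data Management paragraph says "Survey data will be entered into the REDCap system through our website directly by participants"; entry by a facilitator is mentioned only for the initial interview. The prompt is "Email reminders will be sent before each session so that participants will log in at the appropriate time".
- **Saliva.** It is requested from everyone at week 12 and month 6: "Saliva sample kits will be provided via overnight mail with a pre-paid overnight return".
- **Telephone.** Section IV requires participants to "Have a valid telephone number and email address". During follow-up, calls to participants are described for adverse events and for physician questions, not for smoking status.
- **Section IX** says participants return for a session at 6 months, without giving the mode.

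On retention, the sample size text says "Given retention rates from our earlier studies, we expect attrition rates to be approximately 20% over the 6 month study period". The earlier ANBL pilots that report about 80% retention were delivered in person with telephone contact; the larger one had "8 weekly group sessions with individual telephone calls between the group sessions".

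The Primary Aim section gives three analyses: (a) completers only, (b) all participants with dropouts counted as smokers, and (c) all participants with multiple imputation under missing at random. Secondary Hypothesis 2 predicts higher adherence in I-ANBL and models adherence as dropouts versus completers.

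**The concern.** The channel that measures the primary outcome is also the channel that delivers the intervention. A participant can stop using the site, remain enrolled and reachable, and even return the saliva kit, yet give no 7-day self-report. If the sample is consistent with abstinence, the endpoint cannot be scored. That person is then likely to be left out of (a), counted as a smoker in (b), or imputed in (c).

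Two things follow. Missing outcomes would gather among people who disengage from the program, so power and the imputation assumptions both depend on engagement. And because the protocol expects engagement to be better in I-ANBL, the missingness may depend on arm. Analysis (b) would then tend to favour I-ANBL for a reason unrelated to abstinence. The route of collection is fixed in the protocol, so this is not a detail that awaits an analysis plan.

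**Working it through.** **Inputs from the protocol:** abstinence 30% (I-ANBL) v 15% (I-FV), type I error 5%, 121 per group for 80% power, 300 enrolled as 150 per arm, attrition about 20%. **Assumptions made here:** a two-sided test (it reproduces the stated figure), any retention other than 80%, any difference in loss between arms, and a common true abstinence of 22.5% (the midpoint of 15% and 30%) for the bias illustration.

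**Formula.** With n per arm and p̄ = (p1 + p2)/2:

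s0 = √[2p̄(1 − p̄)/n], s1 = √[p1(1 − p1)/n + p2(1 − p2)/n], power = Φ[(|p1 − p2| − 1.96·s0)/s1].

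**Step 1: the plan's own figure.** n = 121: s0 = 0.0537, s1 = 0.0528, (0.15 − 1.96 × 0.0537)/0.0528 = 0.848, power 80.2%. The stated 121 reproduces. Enrolment has no slack: 300 × 0.8 = 240 against the 242 wanted.

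**Step 2: power by retention r, 150 enrolled per arm.** Analysis (a) compares 30% v 15% with n = 150r. Analysis (b) compares 0.30r v 0.15r with n = 150.

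- r = 0.8: (a) n = 120, (0.15 − 1.96 × 0.0539)/0.0530 = 0.836, 79.8%. (b) 24% v 12%, (0.12 − 1.96 × 0.0444)/0.0438 = 0.754, 77.5%.
- r = 0.7 (assumed): (a) n = 105, 74.3%. (b) 21% v 10.5%, 70.6%.
- r = 0.6 (assumed): (a) n = 90, 67.6%. (b) 18% v 9%, 62.7%.

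**Step 3: unequal loss in (b) when there is no true effect.** True abstinence is 22.5% in both arms, and those lost have the same true abstinence as those observed.

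- Loss 10% (I-ANBL) v 30% (I-FV): apparent rates 0.225 × 0.9 = 20.25% and 0.225 × 0.7 = 15.75%. (0.045 − 1.96 × 0.0444)/0.0443 = −0.947, so the chance of a significant result favouring I-ANBL is about 17%, against a nominal 2.5%.
- Loss 15% v 25%: apparent rates 19.1% and 16.9%; the chance is about 7%.

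The inflation depends on some of those lost being abstinent. If everyone lost were a smoker, (b) would classify them correctly and this bias would vanish.

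**The case against.** The best defence is that this is ordinary non-response, already budgeted at 20% and covered by three analyses. All participants are invited at month 6, reminded by e-mail and paid for the survey separately from the weekly sessions. A single web mode in both arms of an internet trial avoids mode effects, and tracing procedures often sit in a manual. Section III lists e-mail follow-up assessments separately from web sessions, Section IX leaves the mode open, and Section X keeps telephone numbers for tracking.

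Much of this limits the point without removing it. None of those three sections gives another way to report smoking status, and Section IX needs reconciling with the 6-Month Follow-Up item. The 20% budget rests on pilots with in-person and telephone contact. A single mode does not help if response through it differs by arm.

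Three stronger readings are tempting, and the documents do not support them:

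- A reader might infer that someone who abandons the website is never asked about smoking. The invitation and e-mail reminder still go out; what is missing is another way to answer.
- A reader might infer that the self-report and sample refer to different days. Both are requested at the month-6 contact, and the interval between them is not stated.
- A reader might infer that every kit returned without a login is wasted. A sample that fails verification already settles the endpoint as not abstinent; only one consistent with abstinence is left unresolved.

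The protocol also does not define a dropout as someone who did not log in, so how such people enter the three analyses is a likely reading, not a stated rule.

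**Conclusion.** The point holds as a weakness in how the primary outcome is collected, and the change should be made. The sample size calculation is not in error: 121 per arm reproduces, and at the planned 80% retention completer power is 79.8%. The slightly lower 77.5% for (b) comes from counting dropouts as smokers, not from the web route.

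What is exposed is the reliance on 80% retention carried over from a different mode of contact, and the prospect of arm-dependent loss that the protocol's own adherence hypothesis raises. The power figures at 70% and 60% retention, and the 17% and 7% false-positive figures, are illustrations under assumed loss; the documents do not predict those losses.

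A reader might also infer that a second route would recover a known share of the missing outcomes and restore a given amount of power. The documents give no figure for how many would be recovered, so no specific gain in retention or power can be claimed.

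**What to change.** Amend the in-person visit and 6-Month Follow-Up items, identically for both arms:

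1. Enclose a dated one-page form with the 7-day smoking question in the week-12 and month-6 saliva kits already mailed to everyone, to be completed on the day of the sample.
2. For anyone who has not logged in, or has not returned the kit, within a fixed number of days, have the existing research assistants telephone to ask the same question and to prompt return of the kit, re-mailing it if needed. A call that only asks about smoking would not be enough, because a claim of abstinence without saliva cannot be verified.
3. Accept the self-report from any route, with the form dated with the sample taking precedence, and still require cotinine verification for abstinence.
4. State the mode of the 6-month session in Section IX so that it agrees with the 6-Month Follow-Up item.

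**Cost:** a wording amendment, one page per kit, some paper data entry, and calls at two time points. At 20% non-response that is 0.20 × 300 = 60 per time point, about 120 in all before repeat attempts. **Downside:** a small mode difference between web, paper and telephone self-report, limited because claimed abstinence still needs cotinine.

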### **Primary Aim/Hypotheses:**

1. To test the effectiveness of the **I-ANBL** compared to the **I-FV** on smoking cessation among tribal college smokers.

Hypothesis 1: At 6 months, participants in the **I-ANBL** group will show higher 7-day point prevalence abstinence rates than those in the **I-FV** group.

We will compare the salivary cotinine verified prevalence abstinence rates at 6 months between the two groups using logistic regression. For our primary comparison, we will conduct per-protocol analyses on (a) only the participants who complete the study, as well as intent-to-treat analyses on (b) all subjects by imputing the dropouts as smokers and (c) all subjects by using the Markov Chain Monte Carlo (MCMC) imputation technique. In (c), the missing data related to attrition can be reasonably assumed to be missing due to known characteristics of our database (i.e., missing at random). We will create a large number of (e.g., 200) complete datasets via expectation-maximization algorithm as prior estimates for the MCMC procedure; and then combine the analysis outcomes from each complete dataset to make valid statistical inferences. To evaluate secondary endpoint, we will compare the salivary cotinine verified prevalence abstinence rates between the groups at Week 12 (end of pharmacotherapy). Finally, as we have no preliminary estimates of relapse based upon timeline follow-back, we will conduct explanatory, failure analyses to compare the time to relapse between the groups. We will calculate failure function (cumulative probability of smoking cessation as a function of time) and fit Cox regression models to the 6-month self-report data on smoking status.

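### The 6-month follow-up rule on repeating the program, read literally, removes only known continuing smokers from the outcome and contradicts the all-randomised analyses

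*Protocol*

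**What the plan says.** The rule stands in Protocol section V, Anticipated Flow of Participants, under 6-Month Follow-Up. Smoking status and a saliva sample are requested at that visit. Then: "Participants who do not report abstinence from smoking use will be asked if they would like to participate in the full program again". Of those who accept, the protocol says "If they choose to participate a second time, they will not be included in" the study outcome measures, and adds that their success will be tracked. The reason given is: "This is done to mimic the real-world situation where a program could be repeated".

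The endpoint belongs to the same visit. Under Sample Size and Power: "The primary endpoint will be cotinine verified 7-day point prevalence abstinence at Month 6".

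Under Primary Aim/Hypotheses, verified abstinence at 6 months is compared "between the two groups using logistic regression". There are three analysis sets. Set (a), called per-protocol, keeps completers only. Set (b), described as intent-to-treat, takes "all subjects by imputing the dropouts as smokers". Set (c) applies multiple imputation to the same full set. None of them mentions participants who repeat the program.

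**The concern.** The grammatical subject of the exclusion is the participant, and nothing limits it to what happens in the second round. Only people who have just reported that they are not abstinent can receive the offer, so everyone the sentence could remove is a failure on the primary endpoint. Nobody who reports abstinence can be removed. Selection of that kind raises the observed quit rate in each arm. It distorts the comparison between arms whenever the share of continuing smokers who repeat is not the same in both.

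The sentence also cannot be followed together with analyses (b) and (c), which take in all subjects. If an analyst reconciled the two by setting repeaters to missing and imputing them under (c), known smokers would acquire a chance of being imputed as abstinent. The exclusion would also thin out the continuing smokers in whom secondary Hypothesis 1A compares cigarette reduction.

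This is not a detail left to a later analysis plan. The protocol itself states both the exclusion and the conflicting analysis sets.

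**Working it through.** **Inputs from the protocol.** Expected quit rates are 30% (I-ANBL) and 15% (I-FV), with 121 per arm for 80% power at a 5% type I error rate (Sample Size and Power). Enrolment is 300, or 150 per arm, with 20% attrition: 150 × 0.80 = 120 completers and 30 dropouts per arm.

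**Input not in the protocol.** The share r of continuing smokers who repeat is not given. All values of r below are assumptions.

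**The plan's own figure.** Two-sided 5%, pooled variance, no continuity correction:

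n = [1.96·√(2 × 0.225 × 0.775) + 0.8416·√(0.30 × 0.70 + 0.15 × 0.85)]² / 0.15² = (1.157 + 0.489)² / 0.0225 ≈ 120.5, so 121 per arm. The stated figure is reproduced; power is 0.802 by formula and about 0.81 by simulation.

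**Effect of the literal rule in completers.** With true quit rate q, the observed rate is q / [q + (1 − q)(1 − r)]. The odds in each arm are divided by (1 − r), so the odds ratio is multiplied by (1 − r_FV)/(1 − r_ANBL).

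**No true effect, q = 20%, 120 completers per arm.** Type I error is simulated with a pooled two-proportion z-test at |z| > 1.96. The last column adds 30 dropouts per arm as smokers, as in analysis (b).

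| r, I-ANBL v I-FV | Observed rates, completers | False odds ratio, completers | Type I error, completers | Type I error, dropouts as smokers |
|---|---|---|---|---|
| 40% v 20% | 29.4% v 23.8% | 0.8/0.6 = 1.33 | about 14% | about 8 to 9% |
| 50% v 20% | 33.3% v 23.8% | 0.8/0.5 = 1.60 | about 28% | about 15% |

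For example, 0.20/(0.20 + 0.80 × 0.60) = 0.294 and 0.20/(0.20 + 0.80 × 0.80) = 0.238.

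Dropouts counted as smokers dilute the bias without removing it. Each arm has 24 quitters. At 50% v 20% the smokers left are 96 × 0.5 + 30 = 78 and 96 × 0.8 + 30 = 106.8, so the false odds ratio is 106.8/78 = 1.37.

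**Uptake the other way round.** At the design rates with r = 20% v 50% and 121 completers per arm, the observed rates are 0.30/(0.30 + 0.70 × 0.80) = 34.9% and 0.15/(0.15 + 0.85 × 0.50) = 26.1%. Simulated power falls from about 0.81 to about 0.23.

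**Equal uptake.** With r = 40% in both arms, 30% v 15% reads as 41.7% v 22.7%. The odds ratio is (0.417/0.583)/(0.227/0.773) = 2.43, the same as (0.30/0.70)/(0.15/0.85) = 2.43. Under no effect the type I error stays near 5%. Power at the design rates falls from 0.81 to 0.77 with r = 30% in both arms, and to between 0.72 and 0.73 with r = 50%.

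**With the first 6-month result kept for everyone.** The false difference is zero in every scenario, type I error is 4 to 5%, and the planned power is preserved.

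**The case against.** The strongest reply is that the authors meant only second-round results. People who have just failed their first round have no success left to track except in the second, so the clause about tracking points that way, as does the stated aim of mimicking real-world repetition. Saliva and smoking status come before the offer, so the Month 6 endpoint already exists when anyone can accept. The analysis section drops no repeaters, and the randomisation visit text keeps participants in their assigned arm. All of this stands. It makes the milder meaning plausible, but no sentence says that a repeater's first 6-month result is retained, and the sentence that exists says something broader.

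A reader might also infer that the rule would favour I-ANBL because it is the cessation program. The protocol does not support a direction. I-FV participants are also offered pharmacotherapy and have a quit date in session 2, so continuing smokers in either arm could have reason to repeat. Unequal uptake is possible, since participants know their arm and the content differs, but neither its size nor its sign is given.

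Finally, the wider gap under equal uptake (19 points instead of 15) might be read as an exaggerated effect. The planned model is logistic, and its odds ratio does not move.

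**Conclusion.** The point holds as a contradiction that must be reconciled. Followed literally, the 6-Month Follow-Up sentence is an exclusion that depends on the outcome, and it cannot coexist with the analyses of all subjects. The documents do not show that the sponsor intends to delete failures, nor that a false benefit would result.

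The size is conditional on two things: that the literal rule is applied, and that uptake differs between arms. Under the assumed uptakes, type I error rises to about 14 to 28% in completers and about 8 to 15% with dropouts counted as smokers. Opposite uptake can hide a real effect, with completer power falling to about 0.23. With equal uptake the harm is limited to inflated quit rates and a modest loss of power. The sample size calculation itself is sound and unaffected.

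**What to change.** Reconcile the 6-Month Follow-Up text with Primary Aim/Hypotheses by replacing the exclusion sentence with:

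> Every randomised participant, including those who later repeat the program, stays in all outcome analyses in the assigned arm, with the first 6-month assessment as the outcome. Missing 6-month assessments are handled as in the Primary Aim analysis. Only data collected after re-entry are excluded from outcome analyses; they are tracked separately.

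The reference to the missing-data rules is needed because some participants will have no 6-month assessment. The cost is this short replacement in the protocol. It needs no additional data and no change in sample size, and if the milder meaning was intended it changes nothing in the planned conduct.
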